7.3	Subject Population(s) for Analysis	19
8	Safety and Adverse Events	19
8.1	Definitions	19
8.2	Recording of Adverse Events	20
8.3	Reporting of Serious Adverse Events and Unanticipated Problems	21
8.3.1	Sponsor-Investigator reporting: notifying the Mayo IRB	21
8.3.2	Sponsor-Investigator reporting: Notifying the FDA	21
8.4	Unmasking/Unblinding Procedures	21
8.5	Stopping Rules	21
8.6	Medical Monitoring	21
8.6.1	Internal Data and Safety Monitoring Board	22
9	Data Handling and Record Keeping	23
9.1	Confidentiality	23
9.2	Source Documents	23
9.3	Case Report Forms	23
9.4	Records Retention	24
10	Study Monitoring, Auditing, and Inspecting	24
10.1	Study Monitoring Plan	24
10.2	Auditing and Inspecting	25
11	Ethical Considerations	25
12	Study Finances	25
12.1	Funding Source	25
12.2	Conflict of Interest	25
13	Publication Plan	25

14 References

25

List of Abbreviations**LIST OF ABBREVIATIONS**

AE	Adverse Event/Adverse Experience
CFR	Code of Federal Regulations
CRF	Case Report Form
DSMB	Data and Safety Monitoring Board
FDA	Food and Drug Administration
GCP	Good Clinical Practice
HIPAA	Health Insurance Portability and Accountability Act
IB	Investigator's Brochure
IND	Investigational New Drug Application
IRB	Institutional Review Board
PHI	Protected Health Information
PI	Principal Investigator
SAE	Serious Adverse Event/Serious Adverse Experience
SOP	Standard Operating Procedure
TKA	Total Knee Arthroplasty
OME	Oral Morphine Equivalents

Study Summary

Title	A Three-Arm, Double-Blinded, Randomized Controlled Trial Comparing the Efficacy of Adductor Canal Pain Catheters following Total Knee Arthroplasty
Running Title	Adductor Catheter Efficacy Following Total Knee Arthroplasty
Protocol Number	Pending
Phase	Phase III
Methodology	Double-Blinded Randomized Controlled Trial
Overall Study Duration	12 months
Subject Participation Duration	60 days, or until discontinuation of narcotic medication (whichever is later)
Single or Multi-Site	Single Center
Objectives	
 • Aim 1 will be to compare postoperative pain levels between groups • Aim 2 will be to compare use of the patient-administered dosing between groups • Aim 3 will be to compare duration of narcotic use between groups
Number of Subjects	84
Diagnosis and Main Inclusion Criteria	Narcotic naïve patients who have a diagnosis of osteoarthritis and are undergoing a primary total knee arthroplasty are eligible for the study.
Study Product, Dose, Route, Regimen	This study will evaluate the efficacy of adductor canal pain catheters following total knee arthroplasty, using either an intermittent bolus or continuous infusion compared to a single-shot adductor canal block.
Duration of Administration	4 days
Reference therapy	Single-shot adductor canal block
Statistical Methodology	Statistical analysis will be performed on the basis of the intention to treat principle. Comparisons between treatment groups will be made using Wilcoxon rank sum test or Fisher's exact test.

1 Introduction

This document is a protocol for a human research study. This study will be carried out in accordance with the applicable United States government regulations and Mayo Clinic research policies and procedures.

1.1 Background

There has been a rapid rise in opioid consumption and deaths in the United States (US) due to opioid use and abuse. In 2017 the Center for Disease Control (CDC) estimated that 72,000 deaths were related to drug overdose, with a large proportion of these stemming from prescription medications. This rate was an approximate two-fold increase over the previous decade and does not include an additional 2 million who are estimated to suffer from a substance abuse disorder related to opioid medications.^{1,2} The high rate of opioid over-prescription following surgery is thought to contribute to the current epidemic.³ In 2014 the National Survey on Drug Use and Health estimated that more than 10 million people in the United States used opioids outside of their prescribed intent, and that 55% of the medication was obtained from a friend or relative.⁴ Therefore, mitigating the amount of narcotics available for diversion is particularly important in order to help combat the opioid crisis.

Orthopedic surgeons are the third highest opioid prescribers (*Combatting Opioid Misuse. 2017. <https://www.aaos.org/AAOSNow/2017/Jun/YourAAOS/youraaos10/?ssopc=1>*). Previous work demonstrated that surgeons prescribe three times the narcotics required by the patient and that most patients do not properly dispose of leftover medication.⁵⁻⁸ Additionally, in a separate study, 13% of narcotic naïve patients became prolonged opioid users following elective orthopedic procedures.⁹ There is a *critical need* to find alternative approaches to postoperative pain management that rely less on narcotic medication.

We previously reported on risk factors for patients requiring additional opioid prescriptions following surgery and have demonstrated that a collaborative approach between the anesthesia and orthopedic teams, utilizing both local and regional nerve blocks, reduced pain scores with a simultaneous 43% decrease in oral morphine equivalents consumed during the hospitalization.^{10,11} Additional studies have focused on multimodal pain regimens, but have not evaluated the efficacy of these regimens with adductor pain catheters.¹²⁻¹⁷ We recently performed a randomized, prospective, double-blinded, placebo-controlled trial using a multimodal regimen with and without schedule II opioids following total knee arthroplasty. In that study we utilized an adductor canal pain catheter with a continuous infusion for four days postoperatively. We demonstrated equivalent postoperative pain scores in the oxycodone and placebo group with use of the adductor catheter. However, despite these similar pain scores, 20% of the oxycodone cohort required continued narcotic medication at 60 days postoperatively (*submitted for publication*).

It is currently unknown if a continuous infusion is the most efficacious form of medication delivery through the catheter. Recent studies have begun to evaluate intermittent bolus infusions, with the belief that catheter placement is less critical when compared to a continuous infusion.

Our study is intended to directly compare these delivery modes in a double-blinded, randomized controlled trial.

1.2 Investigational Agent

This study is not evaluating a specific drug, but rather the safety and efficacy of delivery modes for an adductor canal pain catheter following total knee arthroplasty.

1.3 Clinical Data to Date

Research has focused on prescribing practices, demonstrating the risks of long-term opioid use with large initial prescriptions.^{5,8,20} This has led hospitals to develop institutional guidelines to reduce excessive prescriptions of narcotics following routine surgical procedures. For example, Wyles et al. demonstrated a reduction in the average oral morphine equivalents (OMEs) prescribed at discharge from 750 to 388 following total joint arthroplasty, after departmental adoption of standard prescribing guidelines. Interestingly, the authors reported no increase in refill rates, suggesting that the change largely reduced the amount of unused medication.²¹

At our own center we reported that the number of OMEs prescribed at discharge was not predictive of patients requesting a refill of their medication. We instead found that patients with lower pain scores on postoperative day #1, but not postoperative day #2, had a lower risk of requiring a refill of their pain medication.¹¹ We hypothesized that patients who developed an early reliance on narcotics would be harder to wean from the medication and be at a greater risk of long-term opioid use. Due to this we began to utilize an adductor canal pain catheter for total knee arthroplasty patients to provide improved pain control early in the postoperative period. Following adoption of the adductor canal catheter we reported a subsequent 43% decrease with in-hospital narcotic use.¹⁰ Building upon this we then completed a prospective, randomized, double-blinded, placebo-controlled trial comparing our multimodal regimen with and without schedule II narcotics (oxycodone). In that study we demonstrated equivalent pain scores between the narcotic and placebo group when using a continuous infusion adductor canal pain catheter. The narcotic group, however, had a higher proportion of patients that required pain medication at 60 days postoperatively (*submitted for publication*).

Our goal is to expand upon our previous work and evaluate the safety and efficacy of differing modes of medication delivery with the adductor catheter in order to further optimize postoperative pain control (**Aim 1**). It is hypothesized that intermittent bolus infusions of the medication will provide improved pain control when compared to a continuous infusion due to the ability to more completely saturate the surrounding anatomy in cases where the catheter is not placed in the optimal location adjacent to the nerve. We additionally intend to compare the use of patient-administered dosing (**Aim 2**) and overall duration of narcotic use between cohorts (**Aim 3**).

1.4 Dose Rationale

The dosing of the medications are all currently used following joint replacement procedures.

1.5 Risks and Benefits

The benefits of the study will be to evaluate the efficacy of the differing modes of medication delivery through the adductor canal pain catheter. If optimized, we believe this will allow us to continue to reduce the amount of narcotic medications prescribed following orthopedic surgery.

All components of the multimodal pain regimen are currently safely used in orthopedic patients. There is a theoretical risk of renal damage or GI upset with the use of anti-inflammatory medications, but we have not seen this with our total knee study. There is also the possibility that patients will have uncontrolled pain following surgery. These patients will have IV narcotic medication as a safety net during their hospitalization and will be able to utilize our standard opioid regimen upon discharge.

2 Study Objectives

Primary Objective

The primary objective will be to compare postoperative pain levels between the treatment groups, using the Numerical Rating Scale (NRS).

Secondary Objective

The secondary objectives will be to compare the amount of patient-administered medication use between groups as well as duration of narcotic use between groups.

3 Study Design

This project will be conducted as a three-arm double-blinded, randomized controlled trial comparing differing modes of medication dispersion using the adductor canal pain catheters. The three arms will be a single shot adductor canal block (with saline filled catheter) compared to ropivacaine 0.2% continuous infusion, and ropivacaine 0.2% intermittent bolus infusions. Treatment groups will be assigned to patients using computer-based randomization via the dynamic allocation method of Pocock and Simon. Subjects will be screened in the outpatient clinic setting and those interested and eligible will be consented and enrolled in the trial.

A total of 84 patients will be enrolled in this study. Twenty eight patients will be in each comparison group. After enrollment patients will undergo randomization by the research pharmacy in order to maintain blinding of the surgical team, nursing staff, and patient. The patient will then undergo their surgical procedure and receive a multi-modal pain regimen as described below. All treatment groups will receive the same regimen with the exception of the adductor canal catheter. All of the patients will have the catheter placed in the Post Anesthesia Care Unit following

surgery and bolused with 10 mL of 0.5% ropivacaine. The pumps will be loaded with saline (single shot adductor canal group), or ropivacaine 0.2%, dispersed in either a continuous infusion (6 mL/hr) or pulsed intermittent bolus (8 mL every 2 hours). All groups will have a patient demand dose of 6 mL/hr for anterior knee pain. The medication for the adductor catheter will be dispersed to the anesthesia team by the research pharmacy. The anesthesia team will place the catheter under ultrasound guidance in the recovery room. They will adjust the delivery mode based on patient randomization. The anesthesia team will record the serial number of the pump at the time of placement.

Questionnaires will be sent electronically to the patient. Results will be collected daily for 14 days postoperatively, followed by weekly questionnaires until they discontinue narcotic medications. Additional questionnaires will be collected at 30 and 60 days postoperatively in order to record pain and KOOS Jr. scores. The questionnaires will be sent in the morning; if a patient fails to fill out the questionnaire by the afternoon, a member of the research team will contact the patient to obtain the data. The questionnaires will document numerical rating scale (NRS) pain scores, information on symptoms of nausea, vomiting, and constipation, and will inquire if the patient is still consuming narcotic medication.

Following discontinuation of the catheter the patient will remove and return the device to the supplier. The supplier will then provide the rate of on-demand usage to the research team by way of device serial number. This information will be stored in Redcap.

Subjects will be withdrawn prior to completion if they ask to be removed from the study. They may also be withdrawn from the study if they have a serious adverse reaction to one of the prescribed medications. Finally, subjects may be withdrawn at the discretion of the treating physician. If subjects are withdrawn early their last recorded pain score will be carried forward until study conclusion in order to perform intention to treat analysis. The study will continue to ascertain duration of narcotic use with weekly questionnaires, until the patient has stopped the medication.

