5.3 Method for Assigning Subjects to Treatment Groups

Patients will undergo computer randomization by the research pharmacy prior to dispensing the medication in order to ensure that the treating physician (surgeon) remains blinded to the study.

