7.1 Sample Size Determination

Twenty eight patients will be recruited into each arm, for a total of 84 patients. This number has been chosen for feasibility rather than based on a formal power analysis. We will use this study to provide data for a formal power analysis in order to power a larger study.

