7.2 Statistical Methods

Descriptive and Inferential Statistics

Continuous variables will be summarized with the sample mean, median, standard deviation, minimum, 25th percentile, 75th percentile, and maximum. Categorical variables will be summarized with number and percentage of patients. All analysis will be performed on the basis of the intention-to-treat principle. Comparisons of endpoints between the three treatment arms will be made using a Wilcoxon rank sum test (continuous or ordinal endpoints) or Fisher's exact test (categorical endpoints). Missing data will be imputed using either the last observation carried forward method, a regression-based approach, or another method, depending on the extent of missing data. In order to adjust for the three pair-wise comparisons between treatment groups that will be made for each endpoint, we will utilize a Bonferroni correction for multiple testing, after which p-values of < 0.0167 will be considered as statistically significant. All statistical tests will be two-sided.

Primary Hypothesis:

We hypothesize that the intermittent bolus infusion cohort will report improved pain scores compared to continuous infusion catheters and placebo cohorts.

Secondary Hypothesis:

We hypothesize that the intermittent bolus cohort will require fewer doses of patient-administered medication and will use narcotic medication for a shorter duration when compared to the continuous infusion and placebo groups.

Interim Analysis

We will evaluate the first twenty patients. If 50% of the patients are withdrawn from the study for poor pain control or serious adverse reactions to the study medication, then we will close the study early.

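### Patients are allocated by Pocock-Simon minimisation but compared with tests that ignore the balancing factors; if those factors predict outcome, the tests are conservative and lose power

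*Combined protocol and SAP*

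**What the plan says.** On allocation, section 3 states: "Treatment groups will be assigned to patients using computer-based randomization via the dynamic allocation method of Pocock and Simon". Section 5.3 adds only who does it and when: "Patients will undergo computer randomization by the research pharmacy prior to dispensing the medication". Neither section, nor section 5.8 on blinding, names a balancing factor, a weight or an assignment probability.

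On analysis, section 7.2 states: "Comparisons of endpoints between the three treatment arms will be made using a Wilcoxon rank sum test", with Fisher's exact test for categorical endpoints. The Study Summary says the same. No stratified test, covariate-adjusted model or re-randomisation test is planned. Regression appears only as one option for imputation: "Missing data will be imputed using either the last observation carried forward method, a regression-based approach, or another method".

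On error rate and size, three pairwise comparisons are made per endpoint, "after which p-values of < 0.0167 will be considered as statistically significant". Section 7.1 fixes the numbers: "Twenty eight patients will be recruited into each arm, for a total of 84 patients". It says that they were chosen for feasibility, without a formal power analysis, and that the data will be used to power a larger study.

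**The concern.** Minimisation makes the arms alike on chosen baseline factors. Where those factors influence pain, the difference between arms varies less from one possible allocation to the next than it would under simple randomisation. An unadjusted rank test does not know this. It sets the difference against the full spread of the outcome, including the part that the allocation has already balanced out. Its p-values are then too large on average, and the benefit of balancing never reaches the inference.

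Two things are at stake. First, with 28 per arm and a Bonferroni threshold, each comparison is already strict, and the mismatch makes it stricter without anyone having chosen that. Second, the results are meant to inform the sizing of a later trial. The unadjusted variance exceeds the residual variance by a factor 1/(1 − R²), where R² is the share of outcome variance explained by the factors: 1/0.9 = 1.11, 1/0.8 = 1.25 and 1/0.7 = 1.43. A later trial that analyses with adjustment but is sized from the unadjusted SD would be larger than it needs to be by about those factors.

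**Working it through.** **Inputs from the documents.** Three arms, 28 per arm, 3 × 28 = 84 in total (section 7.1). Threshold 0.0167 for each of three pairwise comparisons (section 7.2), and "All statistical tests will be two-sided". The threshold reproduces: 0.05/3 = 0.01667. There is no power figure to reproduce.

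**Assumed inputs, because the documents give none.** R² from 0 to 0.5; a true difference of 0.75 or 0.8 SD; two or three binary factors; assignment probability 0.8.

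**Step 1, formulas under near-perfect balance.** The critical value is z = 2.394, and the standard error of a difference in SD units is √(2/28) = 0.267.

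- Size of the unadjusted test: 2 × [1 − Φ(z/√(1 − R²))]. At R² = 0.3, 2.394/0.837 = 2.861, which gives 0.0042.
- Power of the adjusted test: Φ(d/(0.267 × √(1 − R²)) − z). At d = 0.75 and R² = 0.3, 3.354 − 2.394 = 0.960, which gives 83%.
- Power of the unadjusted test: Φ((d/0.267 − z)/√(1 − R²)). At the same values, (2.806 − 2.394)/0.837 = 0.492, which gives 69%.

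**Step 2, simulation at 0.75 SD.** 84 patients were allocated by Pocock-Simon with three binary factors. One pairwise comparison was tested by unadjusted Wilcoxon and by a linear model with the factors, with 3,000 to 4,000 trials per cell.

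| R² | Unadjusted size, formula | Unadjusted size, simulated | Power by formula, unadjusted / adjusted | Power simulated, Wilcoxon / adjusted |
|---|---|---|---|---|
| 0 | 1.67% | 1.8% | 66% / 66% | 60% / 62% |
| 0.1 | 1.16% | 1.4% | 67% / 71% | 60% / 68% |
| 0.3 | 0.42% | 0.5% | 69% / 83% | 62% / 82% |
| 0.5 | 0.07% | 0.03% | 72% / 94% | 60% / 93% |

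The Monte Carlo standard error is about √(0.6 × 0.4/3000) = 0.9 points for power and √(0.0167 × 0.9833/4000) = 0.2 points for size. The adjusted test had size 1.4% to 1.9%, consistent with 1.67%. About 2 points of each simulated power gap come from comparing a rank test with a normal-theory test, as the R² = 0 row shows. Under simple randomisation the same Wilcoxon test kept its level (1.3% to 1.8% for R² from 0 to 0.3), so the conservatism comes from the allocation method.

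**Step 3, simulation at 0.8 SD with scores rounded to 0–10 and rank ANCOVA as the adjusted test.** At R² = 0.3, power was 67–68% unadjusted against 83–84% adjusted, with unadjusted size about 0.5%. At R² = 0.1 the gain was 5 to 6 points. At R² = 0 the two tests were within about 2 points.

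**Step 4, detectable difference at 80% power.** (2.394 + 0.842) × 0.267 × √(1 − R²) gives 0.87 SD unadjusted (R² = 0). With adjustment it gives 0.82, 0.72 and 0.61 SD at R² = 0.1, 0.3 and 0.5.

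**Step 5, the choice of adjusted test.** Three crossed binary factors make 2³ = 8 strata for the 56 patients in a pairwise comparison, or 7 per stratum. A van Elteren test across these had power 58% against 66% for the plain Wilcoxon at R² = 0, and 63% against 66% at R² = 0.1.

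**The case against.** The strongest reply is that the loss is conditional and may be negligible. No factor is named, and at low R² there is little to gain: at R² of 0.03 to 0.05, power was 65–67% unadjusted against 68–71% with rank ANCOVA, and about 1.5 points of that gap exist even at R² = 0. This stands. The direction is firm, but the size is not.

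A reader might infer that the 0.0167 threshold is wrong or that false positives are at risk. The documents do not support that. Section 7.2 sets 0.0167 as a Bonferroni cut-off, and the mismatch makes rejection under the null rarer, not more frequent.

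A reader might also infer that the trial falls short of its planned power. It has none: sections 3.2 and 7.1 describe a pilot sized for feasibility. This lowers the priority but does not dispose of the point. The Study Summary labels the trial Phase III, section 7.2 states directional hypotheses and a significance threshold, and with the sample size fixed, the efficiency of the analysis is one of the few things that can still be improved.

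Finally, adjustment is not automatically better. A fully stratified rank test can do worse than the planned one, as step 5 shows. That limits which remedy to use.

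**Conclusion.** The design and the analysis do not match: allocation uses balancing factors, and no planned comparison does. If the factors predict the outcome, the planned tests are conservative and lose power.

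For an assumed difference of 0.75 to 0.8 SD at 28 per arm, the loss is near nil at R² = 0, about 5 to 8 points of power at R² = 0.1, and about 15 to 20 points at R² = 0.3, where true size is about 0.5% against a nominal 1.67%. These figures rest on assumed R², effect size, number of factors and assignment probability, and cannot be narrowed until the sponsor names the factors.

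The point is a low-cost gain in efficiency. The planned tests do not overstate the evidence, and no figure in the documents is refuted.

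**What to change.** Before unblinding, list in section 7.2 the factors used by the allocation program, with their levels and the assignment probability. The method cannot run without factors, but the documents do not show what they are, so the sponsor must supply them. Section 8.4 unblinds patients who are withdrawn early, which is a reason to settle the list soon.

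- **Continuous and ordinal endpoints:** include the factors as main effects in each pairwise comparison. Use rank ANCOVA (ranked endpoint on arm plus factors) for the test at 0.0167. Add a linear model on the NRS scale to give the adjusted mean difference, because section 3.4 promises a mean difference and rank ANCOVA does not provide one.
- **Van Elteren test:** do not use it across fully crossed factors unless there are very few strata.
- **Binary endpoints:** use a factor-adjusted or stratified test only where the strata are not sparse. Otherwise keep Fisher's exact test. The calculations above did not examine binary endpoints.
- **Sensitivity analyses:** keep the unadjusted Wilcoxon and Fisher tests.
- **For the later trial:** report the residual SD alongside the unadjusted SD.

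The cost is a few degrees of freedom, some SAP wording and a few lines of code, with no extra patients.

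### The bolus–continuous contrast compares two regimens whose programmed ropivacaine dose differs by a third (8 vs 12 mg/hr), so it does not isolate delivery mode

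*Combined protocol and SAP*

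**What the plan says.** The question is framed as one about mode in several places. Section 1.1: "Our study is intended to directly compare these delivery modes in a double-blinded, randomized controlled trial". Section 1.2: "This study is not evaluating a specific drug, but rather the safety and efficacy of delivery modes". Section 3 describes the trial as "comparing differing modes of medication dispersion using the adductor canal pain catheters". Section 1.3 gives a mechanism specific to mode, namely that intermittent boluses "will provide improved pain control when compared to a continuous infusion due to the ability to more completely saturate the surrounding anatomy" when the catheter is not ideally placed.

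The settings are in section 3. The anesthesia team places the catheter, and "They will adjust the delivery mode based on patient randomization". Both active arms receive ropivacaine 0.2%, "dispersed in either a continuous infusion (6 mL/hr) or pulsed intermittent bolus (8 mL every 2 hours". The loading bolus and the patient demand setting (6 mL/hr) are the same in all three groups.

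The only dose rationale, section 1.4, reads: "The dosing of the medications are all currently used following joint replacement procedures". Sections 5.1 and 5.2 refer back to section 3.1, which gives no catheter rate. Section 7.2 does not mention the difference.

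Two stated comparisons set bolus against continuous: the primary hypothesis on NRS pain (sections 3.4 and 7.2), and the patient-administered dosing endpoint ("Aim 2 will be to compare use of the patient-administered dosing between groups"), for which sections 3.5 and 7.2 predict fewer demand doses with bolus.

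**The concern.** A comparison of modes needs the arms to differ in how the drug is delivered and otherwise be alike. Here the pump settings change the pattern of delivery and the scheduled hourly dose together, and the protocol acknowledges only the first.

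This matters for interpretation. If bolus shows no advantage, or does worse, the protocol's own framing leads to the conclusion that intermittent delivery does not help. The same result could arise if bolus delivery does help and the smaller background dose offsets it. Demand use has the same difficulty: patients on a lower background dose may press the button more often, whatever the mode. Section 7.1 says the data will be used to power a larger study. An estimate from this trial carries over as a contrast of these two regimens if both rates are kept, but not as an effect of mode.

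**Working it through.** The plan states no hourly figure for the bolus arm and no mg/hr figure for either arm, so there is no stated result to reproduce.

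**Inputs**
- Continuous rate: 6 mL/hr (section 3).
- Bolus setting: 8 mL every 2 hours (section 3).
- Concentration: 0.2% = 2 mg/mL in both active arms (section 3).
- Loading bolus: 10 mL of 0.5% ropivacaine = 50 mg in every arm (section 3). It adds the same amount to each arm and is left out below.
- Demand setting: 6 mL/hr in every arm (section 3), read here as up to 6 mL in any hour.
- Duration of administration: 4 days = 96 h (Study Summary).

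**Programmed dose**
- Continuous: 6 × 2 = 12 mg/hr; × 24 = 288 mg per 24 h (144 mL).
- Bolus: 8 / 2 = 4 mL/hr; 4 × 2 = 8 mg/hr; × 24 = 192 mg per 24 h (96 mL).
- Relative gap: 1 − 4/6 = 33.3%.
- Over 96 h with no demand use: 1152 mg vs 768 mg, a difference of 384 mg.

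**With equal demand use of d mL/hr in both arms**, the gap is 1 − (4 + d)/(6 + d):

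| d (mL/hr) | Continuous (mg/hr) | Bolus (mg/hr) | Gap |
|---|---|---|---|
| 0 | 12 | 8 | 33.3% |
| 1 | 14 | 10 | 28.6% |
| 2 | 16 | 12 | 25.0% |
| 3 | 18 | 14 | 22.2% |
| 6 | 24 | 20 | 16.7% |

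**Demand needed to equalise total dose:** 6 − 4 = 2 mL/hr more with bolus, or 48 mL per 24 h. That is one third of the 6 mL/hr setting, and it runs against the stated hypothesis of fewer demand doses with bolus.

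**What the contrast identifies.** Let B(4) and C(6) be mean pain under the two programmed regimens, and C(4) mean pain under a continuous infusion at 4 mL/hr, with demand dosing available in each. Then

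B(4) − C(6) = [B(4) − C(4)] + [C(4) − C(6)].

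The first bracket is the mode effect at equal programmed dose, the second the effect of the lower dose. The trial estimates only the sum.
- If more drug is no worse for pain, the second bracket is zero or positive. A negative sum (bolus better) then implies a negative first bracket, so the direction of the mode effect is supported, but its size is not identified.
- A sum near zero or above is compatible with a mode benefit, no mode effect or a mode harm.

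The same split applies to demand use. If bolus patients use more, mode and lower background dose are both candidate explanations.

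**The case against.** The strongest reply is that nothing in the planned analysis is invalid. The primary objective in section 2 compares pain between treatment groups, the hypotheses compare cohorts, section 7.2 tests the three arms, and both rates are stated openly. Comparing two regimens as programmed is a legitimate design. The lower dose also sits in the arm expected to do better, so under the usual assumption about dose the gap works against the hypothesis. With 28 per arm, no power analysis, and a trial described as a feasibility pilot, a null pain result would be weak evidence even at equal rates.

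Most of this stands, and it limits the point to interpretation. It does not remove it: sections 1.1, 1.2, 1.3 and 3 promise a statement about mode, and the settings do not support one in the null or adverse case. The generic sentence in section 1.4 does not explain why the arms differ.

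Three stronger readings are tempting and should be resisted.
- A reader might infer that the bolus–continuous comparison is statistically invalid. It is not; randomisation supports the regimen contrast, and each contrast with saline is unaffected.
- A reader might infer that a bolus win would be uninterpretable. It would not be, provided more drug is no worse for pain.
- A reader might infer from section 5.9.4, which links catheter removal to the drug being used up, that infusion duration also differs by arm. No fill volume is given, and the Study Summary (4 days) and section 5.9.4 (postoperative day 4) make no distinction between arms.

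**Conclusion.** The point holds as a limit on what the trial can conclude. Programmed ropivacaine is 33% lower with bolus (8 vs 12 mg/hr; 192 vs 288 mg per 24 h), without acknowledgement or explanation. The contrast therefore estimates a difference between two regimens and not the effect of delivery mode. The programmed figures rest only on the stated rates and concentration. The figures with demand use assume equal use in both arms, and the 96-hour totals assume four full days with no demand use. How far the dose gap would move NRS pain cannot be computed from the documents, so no clinical size is claimed. The correction is worth making because it changes the conclusion that may be drawn at almost no cost.

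**What to change.** In the objective, the hypotheses and the eventual conclusion, state:

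> The bolus–continuous contrast compares two programmed regimens of ropivacaine 0.2% with unequal background dose (8 mg/hr as 8 mL every 2 hours, and 12 mg/hr as 6 mL/hr). Differences, or their absence, will not be attributed to delivery mode alone.

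Give the reason for the two rates in section 1.4. Report total ropivacaine delivered (programmed plus demand, per 24 h) descriptively in the two active arms.

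Cost: wording, plus one descriptive summary. Section 3 already has the supplier return on-demand usage by device serial number; pump run time is not mentioned there and may need an added request. The downside is a narrower headline claim.

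Equalising the hourly rates is optional and a clinical choice. Arithmetically it could be 12 mL every 2 hours (12 / 2 = 6 mL/hr), 8 mL every 80 minutes (8 / 6 h = 80 min), or continuous infusion at 4 mL/hr. Any of these needs a changed pump setting and a protocol amendment, and the documents do not show that these particular settings are in current use.
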